### 4.3 Additional Outcome Measures

- 1) Event rates of the following TAVI-related complications:
  - change to surgery
  - o need for cardiopulmonary mechanical assistance
  - coronary occlusion or obstruction
  - annular rupture or dissection
  - ventricular perforation
  - mitral valve damage
  - o prosthetic valve displacement, migration, or embolism
  - acute kidney injury (up to 7 days post procedure)
- 2) All-cause mortality at 6 months, one year, and annually through 5 years
- 3) All stroke (disabling and non-disabling) at 6 months, one year, and annually through 5 years
- 4) Myocardial infarction at 30 days, 6 months, one year, and annually through 5 years
- 5) Life-threatening bleeding at 30 days, 6 months, one year, and annually through 5 years
- 6) New AV-Conduction disturbances (LBBB and RBBB) at 30 days
- 7) Prosthetic valve endocarditis at 30 days, 6 months, one year, and annually through 5 years
- 8) Prosthetic valve thrombosis at 30 days, 6 months, one year, and annually through 5 years
- 9) Valve-related dysfunction, defined as moderate or severe prosthetic valve stenosis, or moderate or severe prosthetic regurgitation (per VARC II) at one year and annually through 5 years
- 10) Valve-related dysfunction requiring repeat procedure at 30 days, 6 months, one year, and annually through 5 years
- 11) Valve hemodynamic performance metrics by Doppler echocardiography at one year and annually through 5 year
  - Mean aortic gradient
  - Effective orifice area
  - Degree of aortic regurgitation (transvalvular, paravalvular, total)

Revision 3.0 Page 8 of 23

- 12) New York Heart Association (NYHA) functional classification at 30 days, 6 months, one year and annually through 5 years
- 13) Post-operative EQ-5D quality of life at 30 days and one year

#### 5. **Investigation Plan**

This is a prospective, single arm, multi-center, interventional, post-market study. Subjects will be consented for follow-up through 5 years. The enrollment phase of the study was completed; the estimated total duration of the study (first subject enrolled to last subject completing his/her last followup visit) is estimated to be 6.5 years, excluding the time required for preparing the study start-up, final report and study closure.

The study will be conducted at approximately 6 centers with a maximum of 8 centers in China with approximately 65 subjects with a maximum of up to 70 subjects with an attempted implant using the Evolut PRO system. There is no minimum number of subjects required for each clinical institution. No site will implant more than 20 subjects, excluding the roll-in subjects, without prior authorization from Medtronic. By completion of the enrollment phase, 58 attempted implanted subjects from 4 activated sites were enrolled.

Subjects who are taken to the procedure room for implantation but do not receive an Evolut PRO for any reason will be exited from the study within 30-days post the date of implant procedure unless a study system and/or implant procedure related Adverse Event (AE) is identified. If a study system and/or implant procedure related AE is identified, the subject will be followed until the event is resolved or no further actions need to be taken. In the rare event the Evolut PRO TAV is explanted from the subject, their participation in the study ends following discharge from the explant hospitalization or 30 days post-explant, or through resolution of potential related adverse events (whichever comes later) to assess safety and then terminated from the study.

Estimating 65 subjects with a maximum of up to 70 subjects in China with an attempted implant, comprised of the following:

- 1) Primary study population: 50 subjects with an attempted implant using the Evolut PRO system
- 2) Roll-in population: The first two attempted subjects at each site will be considered "roll-in" subjects. The maximum number of roll-in subjects among all sites will be 20 subjects. The roll-in population will be followed per the same protocol as the primary study population; however, results from the roll-in population will be analyzed separately from the primary study population.

[figure not shown]
#### 5.1 Measures to Minimize Bias

The study methods include the following measures to minimize potential sources of bias:

- An Eligibility Review Committee (ERC) will confirm subject eligibility and anatomical suitability.
- An independent Clinical Events Committee (CEC) will review and adjudicate, at minimum, all deaths and endpoint related adverse events. Safety endpoint results will be based on CEC adjudications.

Revision 3.0

Page 9 of 23

- All sites will follow a standardized protocol for acquisition of echocardiographic endpoint data.
- An independent Echo Core Lab will evaluate all echocardiograms through the 30-days follow up assessment. Echocardiographic study endpoint results through 30 days will be based on core lab assessments.
- Study sites should follow their institutional procedures for maintenance of echocardiography and laboratory equipment used for assessing the study variables.

#### 5.2 Inclusion and Exclusion Criteria

#### **Inclusion criteria**

Prospective subjects must meet all of following inclusion criteria to be eligible for implantation:

- 1. Severe aortic stenosis, defined as aortic valve area of <1.0 cm^2 (or aortic valve area index of <0.6 cm^2/m^2) by the continuity equation, OR mean gradient >40 mmHg OR maximal aortic valve velocity >4.0 m/sec by resting echocardiogram
- 2. High risk for SAVR defined as STS-PROM score  $\geq$  8% AND  $\leq$  15%, OR documented Heart Team agreement of high risk for AVR due to frailty or comorbidities
- 3. Symptoms of aortic stenosis AND NYHA Functional Class II or greater
- 4. The subject and the treating physician agree that the subject will return for all required post procedure follow-up visits

[figure not shown]
#### **Exclusion criteria**

If any of the following exclusion criteria are present, the prospective subject is not eligible for implantation:

- 1. Any condition considered a contraindication for placement of a bioprosthetic valve (e.g., subject is indicated for mechanical prosthetic valve)
- 2. Age is less than 65 years
- 3. A known hypersensitivity or contraindication to any of the following which cannot be adequately pre-medicated: • aspirin or heparin (HIT/HITTS) and bivalirudin • ticlopidine and clopidogrel • nitinol (titanium or nickel) • contrast media
- 4. Blood dyscrasias as defined: leukopenia (WBC <1000 mm³), thrombocytopenia (platelet count <50,000 cells/mm^3), history of bleeding diathesis or coagulopathy, or hypercoagulable states
- 5. Untreated clinically significant coronary artery disease requiring revascularization
- 6. Severe left ventricular dysfunction with left ventricular ejection fraction (LVEF) < 20% by echocardiography, contrast ventriculography, or radionuclide ventriculography
- 7. End stage renal disease requiring chronic dialysis or creatinine clearance <20 cc/min.
- 8. Ongoing sepsis, including active endocarditis
- 9. Any percutaneous coronary or peripheral interventional procedure with a bare metal or drug eluting stent performed within 30 days prior to study procedure

Revision 3.0

Page 10 of 23

[figure not shown]

- 10. Symptomatic carotid or vertebral artery disease or successful treatment of carotid stenosis within 10 weeks of enrollment
- 11. Cardiogenic shock manifested by low cardiac output, vasopressor dependence, or mechanical hemodynamic support
- 12. Recent (within 6 months of Heart Team assessment) cerebrovascular accident (CVA) or transient ischemic attack (TIA)
- 13. Gastrointestinal (GI) bleeding that would preclude anticoagulation
- 14. Subject refuses a blood transfusion
- 15. Severe dementia (resulting in either inability to provide informed consent for the study/procedure, prevents independent lifestyle outside of a chronic care facility, or will fundamentally complicate rehabilitation from the procedure or compliance with follow-up visits)
- 16. Estimated life expectancy of less than 12 months due to associated non-cardiac co-morbid conditions
- 17. Other medical, social, or psychological conditions that in the opinion of the investigator precludes the subject from appropriate consent or adherence to the protocol required follow-up exams
- 18. Currently participating in an investigational drug or another device study (excluding registries)
- 19. Evidence of an acute myocardial infarction  $\leq$  30 days before the study procedure
- 20. Need for emergency surgery for any reason
- 21. Liver failure (Child-Pugh class C)
- 22. Patients requiring TAV implantation via carotid aortic access
- 23. Currently undergoing radiation therapy

#### Anatomical exclusion criteria:

- 24. Pre-existing prosthetic heart valve in any position
- 25. Mixed aortic valve disease (aortic stenosis with severe aortic regurgitation with predominant aortic regurgitation > 3+)
- 26. Severe mitral regurgitation
- 27. Severe tricuspid regurgitation
- 28. Moderate or severe mitral stenosis
- 29. Hypertrophic obstructive cardiomyopathy
- 30. Echocardiographic or Multi-Detector Computed Tomography (MDCT) evidence of intracardiac mass, thrombus, or vegetation
- 31. Non-calcified aortic valve
- 32. Unicuspid valve verified by echocardiography
- 33. Bicuspid aortic valve with no raphe or 2 raphes (Sievers classification type 0 or type 2)
- 34. Sinus of Valsalva diameter unsuitable for placement of the self-expanding bioprosthesis

Revision 3.0 Page 11 of 23

- 35. Aortic annulus diameter of < 18 or > 26 mm.
- 36. Significant ascending aortopathy requiring surgical repair
- 37. Ascending aorta diameter > 4.5 cm
- 38. For transfemoral access vessel diameter < 5.5 mm or for transaxillary (subclavian) access < 6.0 mm in patients with a patent left internal mammary artery (LIMA)

### 5.3 Schedules and Visit Window

|                                       | Screening                       |             | Index Hospitalization |                             |           | Follow-up Assessments |                                 |                 |                          |
|---------------------------------------|---------------------------------|-------------|-----------------------|-----------------------------|-----------|-----------------------|---------------------------------|-----------------|--------------------------|
| Event                                 | Baseline
(Local
screening | (Local (FRC | Implant               | 24
Hours
to 7
Days | Discharge | 30
Days            | 6
Months                     | 1
Year       | 2-5
Years
Annually |
|                                       | prior to                        |             |                       |                             |           | Clinic
Visit       | Subject
Contact  | Clinic
Visit | Clinic
Visit          |
| Clinical                              | х                               |             |                       |                             | X²        | х                     | х                               | х               | х                        |
| assessment                            |                                 |             |                       |                             |           |                       |                                 |                 |                          |
| Aes, SAEs and                         |                                 |             |                       |                             |           |                       |                                 |                 |                          |
| Device-related
events  | ×                               | х           | х                     | х                           | х         | x                     | x                               | х               | x                        |
| MDCT                                  | X                   |             |                       |                             |           |                       |                                 |                 |                          |
| TTE                                   | Х                               |             |                       | χs                          |           | х                     |                                 | х               | Х                        |
| Heart Team                            | х                               |             |                       |                             |           |                       |                                 |                 |                          |
| Assessment                            | ^                               |             |                       |                             |           |                       |                                 |                 |                          |
| 12-lead ECG                           |                                 | Х           |                       |                             |           | Х                     |                                 |                 |                          |
| Modified                              |                                 | х           |                       |                             |           |                       |                                 |                 |                          |
| Rankin score              |                                 | ^           |                       |                             |           |                       |                                 |                 |                          |
| Aortography                           |                                 |             | Х                     |                             |           |                       |                                 |                 |                          |
| EQ-5D                                 |                                 | Х           |                       |                             |           | х                     |                                 | Х               |                          |

<sup>1Subject contact includes phone call, email or clinic visit

#### Visit Windows

Within 12 weeks prior to Eligibility Review Committee review Baseline

Discharge Discharge from index procedure or 7 days post implant, whichever comes first

30 Days Between 30 and 45 days post implant 6 Months Between 183 and 210 days post implant 1 Year Between 365 and 395 days post implant

2-5 Years Between implant anniversary date and 30 days after

<sup>2 NYHA assessment is not required at discharge

<sup>3 Events are collected after the time of enrollment (i.e., written informed consent obtained)

[figure not shown]
 Pre-implant MDCT must be within 365 days of planned implant date

TTE for device success should be performed within 24 hours to 7 days post procedure

 Modified Rankin score assessment should be conducted at 1 and 3 months following the date of a stroke event

Revision 3.0

Page 12 of 23

## 6. Determination of Sample Size

As this is not a powered hypothesis-driven study, the sample size of 50 attempted subjects was not determined by statistical methods. Rather, it was based on adherence to the NMPA TAVI Clinical Trial Guideline and was confirmed during the NMPA consultation meetings and protocol synopsis submitted with no further objections/feedback (October 2018 through March 2019).

The total sample size of the primary study population is 50 attempted implants, exclusive of the roll-in population. There is no minimum number of subjects required for each clinical institution. No site will implant more than 20 subjects, excluding the roll-in subjects, without prior authorization from Medtronic.

## 7. Statistical Methods

## 7.1 Study Subjects

## 7.1.1 Disposition of Subjects

The distribution of enrolled subjects table will be used to summarize the disposition of enrolled subjects. Number of subjects consented, number of subjects enrolled, number of subjects with an attempted implant, and number of subjects implanted will be reported.

## 7.1.2 Clinical Investigation Plan (CIP) Deviations

Protocol violations (study deviations) will be reported to Medtronic throughout the study by each site and identified through monitoring activities.

Deviations will be summarized by type for each interval. The percent of subjects with the deviations will be calculated based on the number of subjects eligible for the specified visit (e.g., screening, enrollment, index procedure).

## 7.1.3 Analysis Sets

The two main analysis sets for this study are defined as follows:

- Attempted implant set: Includes all subjects who are brought into the procedure room and any
  of the following have occurred: anesthesia administered, vascular line placed, TEE placed, or any
  monitoring line placed.
- Implanted set: Includes all subjects who are implanted with the Evolut PRO, defined as the
  Evolut PRO is placed in the aortic annulus and completely released from the delivery catheter
  system.

[figure not shown]
Index procedure (TAVR) is defined as the first procedure that the Medtronic EnVeo™ PRO Delivery Catheter System is introduced.

Figure 2. Analysis sets for the study endpoints

Revision 3.0

Page 13 of 23

**Roll-in population**: The first two attempted subjects at each site will be considered "roll-in" subjects. The maximum number of roll-in subjects among all sites will be 20 subjects. The roll-in population will be followed per the same protocol as the primary study population (n= 50 subjects with attempted implant, exclusive of "roll-in" patients); however, results from the roll-in population will be analyzed separately from the primary study population.

Additionally, a per-protocol set was defined as follows:

[figure not shown]
- Per-Protocol set: Includes all subjects who are implanted, with evaluable primary endpoint, and
  no major protocol deviation. Possible major protocol deviations may include but not limited to,
  in a priority queue, missing primary safety endpoint or primary efficacy endpoint, using nonstudy device, violating inclusion/exclusion criteria, out of time window assessment (e.g., 30-day
  echocardiogram performed earlier than the start of the visit window). Protocol deviations will
  be listed and reviewed in the blind data review meeting (if applicable) before the final hard lock.
   Exclusion from the per-protocol set will be finalized and documented prior to the primary
- Statistical analysis will be performed when the primary study population (n= 50 subjects with attempted implant, exclusive of "roll-in" patients) are followed for 30 days.

endpoint hard lock. Any Per-Protocol set analysis will be provided separately as needed.

The primary analysis for the primary safety objective, secondary safety objectives, device success, and the additional outcome measures of safety outcomes, NYHA and quality of life will use the attempted implant set. Primary efficacy endpoint, valve performance, and other outcome measures related to valve dysfunction, and hemodynamic performance metrics will use the implanted set.

Revision 3.0

Page 14 of 23

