#### Endpoint Definition/Parameters to Be Estimated:

The endpoint is the KM event rate of all-cause mortality at 30 days post procedure.

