#### Data Collection and Analysis Method:

Data will be collected in the ECHO CORE LAB CRF at 30-days post procedure. Frequency and percent of moderate or severe aortic regurgitation will be analyzed. To calculate the percent of moderate or severe aortic regurgitation, the numerator will be the number of patients with total Aortic Prosthetic Regurgitation on the ECHO CORE LAB CRF equals to moderate, moderate to severe, and severe at 30-day post procedure, and the denominator will be the number of patients whose 30-day total aortic regurgitation are not missing.

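### Applied as written, the per-protocol criteria in SAP 7.1.3 exclude anyone who dies before day 30, so any per-protocol 30-day mortality figure would be essentially 0% whatever happened

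*SAP*

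**What the plan says.** SAP 7.1.3 names two main analysis sets, attempted implant and implanted, and adds a per-protocol set. The entry rule is: "Includes all subjects who are implanted, with evaluable primary endpoint, and" no major protocol deviation.

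The deviation list is introduced permissively: "Possible major protocol deviations may include but not limited to". First on it is "in a priority queue, missing primary safety endpoint or primary efficacy endpoint". Out-of-window assessment is also listed, with the 30-day "echocardiogram performed earlier than the start of the visit window" as the example. Exclusions are to be settled and documented before the hard lock for the primary endpoint. Per-protocol analyses are optional, and no endpoint is named for them.

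The related definitions are:

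- **30-day visit window** (SAP 5.3, and the same in Protocol 9.2.4, Table 3 and Appendix II): "Between 30 and 45 days post implant".
- **Primary safety endpoint** (SAP 7.10.1): "The endpoint is the KM event rate of all-cause mortality at 30 days post procedure", analysed in the attempted implant set.
- **Primary efficacy endpoint** (SAP 7.10.2): a percentage for which "the denominator will be the number of patients whose 30-day total aortic regurgitation are not missing". There is no rule for a subject who died before the echo.
- **Missing data** (SAP 7.4): a subject with missing data is left out of that portion of the analysis, whatever the reason.

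**The concern.** A per-protocol set should select on adherence to the plan. Here one set is defined by reference to both primary endpoints, and lacking either one is a listed ground for exclusion. A subject who dies in the first month has a fully observed primary safety endpoint, but has no 30-day echo because of that death. Counting the absent echo as a deviation removes the subject because of the safety outcome itself.

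A per-protocol mortality table built this way would look like corroboration of the main result but could not show an early death. The Protocol (sections 6 and 22) says the study data and reports may support registration of later device generations or expanded indications, so a supportive table of this kind could be read outside the trial team.

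**Working it through.** The documents give no per-protocol mortality figure, no death count and no power calculation, so there is no stated result to reproduce. The check has two parts.

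**1. Can a subject who dies by day 30 be in the set?**

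Inputs: the window of days 30 to 45 (SAP 5.3), and the listed deviations for a missing efficacy endpoint and an early echo (SAP 7.1.3). Applied as written, these require an echo on a day *E* with 30 ≤ *E* ≤ 45. An echo cannot follow death, so *E* ≤ *D*, where *D* is the day of death.

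- If *D* ≤ 29, then *E* ≤ 29. The echo is either absent (first listed deviation) or before the window (also listed). The subject is out.
- If *D* = 30, the only admissible echo day is *E* = 30. The subject stays in only with an echo and death on the same day.

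Enumerating death days 0 to 60 against echo days 1 to 60 gave the same answer: the only member of the set with a death by day 30 is the pair (*D*, *E*) = (30, 30).

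**2. How large could the gap be?**

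Assumptions: *d* deaths, all before day 30; all 50 subjects of the primary population implanted; no other per-protocol exclusions. The attempted implant set then gives *d*/50 and the per-protocol set gives 0/(50 − *d*).

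Intervals are exact (Clopper-Pearson) 95%. The limits are the Beta(*x*, *n* − *x* + 1) quantile at 0.025 and the Beta(*x* + 1, *n* − *x*) quantile at 0.975. For *x* = 0 the upper limit is 1 − 0.025^(1/*n*); for example, 1 − 0.025^(1/48) = 7.4%.

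The log-log Kaplan-Meier interval of SAP 7.2.2, without censoring, is S^exp(±1.96·se), with S = 1 − *d*/50 and se = √[*d*/(50(50 − *d*))]/|ln S|. For *d* = 2: S = 0.96 and se = 0.0289/0.0408 = 0.707, which gives mortality limits of 1.0% and 15.1%.

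| Assumed deaths before day 30 | Attempted implant set | Exact 95% CI | KM log-log 95% CI | Per-protocol, criteria as written | Exact 95% CI |
|---|---|---|---|---|---|
| 1 | 1/50 = 2.0% | 0.1–10.6% | 0.3–13.4% | 0/49 = 0% | 0–7.3% |
| 2 | 2/50 = 4.0% | 0.5–13.7% | 1.0–15.1% | 0/48 = 0% | 0–7.4% |
| 3 | 3/50 = 6.0% | 1.3–16.5% | 2.0–17.5% | 0/47 = 0% | 0–7.5% |

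The chance that there is at least one death to lose is 1 − (1 − *q*)^50 for true 30-day mortality *q*. For assumed *q* of 1%, 2%, 4% and 6% it is 39.5%, 63.6%, 87.0% and 95.5%.

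**The case against.** Much of the case on the other side stands.

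- **The list is discretionary.** Its items are possible deviations, and exclusions are settled at data review. The SAP nowhere says that death before the echo is a major deviation. A reader might infer that the SAP fixes per-protocol mortality at 0%. The text does not support that; the result follows only if the listed items are applied as written.
- **The entry rule is singular.** It asks for an evaluable primary endpoint although there are two, and a death is an evaluable safety endpoint. An endpoint-by-endpoint reading would keep early deaths.
- **Death is not an obvious deviation.** Protocol 17.1 treats a deviation as a failure to follow the plan, although its examples include missed visits and tests. SAP 7.1.2 bases deviation percentages on subjects eligible for the visit, and a subject who has died is hardly eligible.
- **No per-protocol mortality analysis is specified.** SAP 7.1.3 and 7.10.1 assign 30-day mortality to the attempted implant set. The sensitivity analyses in 7.10.1 (complete, worst-case, best-case, tipping-point) do not use the per-protocol set. SAP 7.10.5 assigns mortality from 6 months to 5 years to the attempted implant set too. A reader might infer that 5-year mortality is affected; no planned analysis supports that.
- **Timing.** The primary analysis is complete, and Protocol 10.8 says that analysis sets should in principle not change.

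These points limit the reach of the problem but do not remove it. The deviation list joins the two primary endpoints with an or, so one missing endpoint is a listed ground for exclusion. The two readings give different mortality figures, and the SAP does not choose between them. Leaving the choice to data review is weak protection in a single-arm study, where those deciding may know who died and the blind review meeting is itself conditional.

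**Conclusion.** The point holds in a limited form. With the criteria applied as written, survival to day 30 is in effect a condition of entry to the per-protocol set. Any 30-day mortality figure from it would be essentially 0% regardless of the true number of early deaths, apart from a death on day 30 after a same-day echo. The understatement would equal the observed pre-day-30 mortality, for example 4.0% shown as 0%. That size rests on assumed deaths, full implantation and no other exclusions.

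The primary mortality result and the later mortality results are untouched, because both use the attempted implant set. There is no pass/fail criterion that a per-protocol figure could sway. What is at risk is an optional supportive analysis, and the documents do not show that one was ever produced for mortality. The clarification is still worth making, because the stated criteria select on the primary safety outcome and the correction costs almost nothing.

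**What to change.** In SAP 7.1.3, do one of the following:

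- state that death by day 30 is an evaluable primary safety endpoint, and that an echo missing because of death is not a per-protocol exclusion for safety; or
- restrict the per-protocol set to the efficacy endpoint, and report how many subjects were excluded because they died before the echo.

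If the single set has already been used for 30-day mortality, keep it as locked and label the figure as conditional on survival to the 30-day echo.

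The cost is a sentence or short paragraph in the SAP and, at most, one relabelled or rerun table, with no new data. There are two drawbacks. Any per-protocol mortality figure may become less favourable. A change made after the primary analysis must also be documented as such, in line with Protocol 10.8.
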